Study procedures	Visit 1 Screening Day -28 to-1	Visit 2 Baseline Day 1	Visit 3 Phone Day 15 ±1	Visit 4 In Clinic Day 29 ±2	Visit 5 In Clinic Day 43 ±2	Visit 6 In Clinic Day 85 ±3	Visit 7 In Clinic / End of Acthar Taper Day 113 ±3	Early Termination
Superior, central and total corneal staining score (fluorescein)	X	X		X	X	X		X
Nasal, temporal and total conjunctival staining score (lissamine green)	X	X		X	X	X		X
Schirmer's Test	X	X		X	X	X		X
IOP	X					X	X	X
Undilated Fundoscopy	X					X	X	X
Inclusion/Exclusion criteria review	X	X						
Height ^a and weight	X	X				X	X	X
Vital signs ^b	X	X		X	X	X	X	X
Physical examination	X					X		X
Laboratory testing								
Chemistry and others ^c	X	X		X	X	X		X
HbA1c	X	X		X	X	X		X
Serum Pregnancy	X	X		X	X	X		X

Study procedures	Visit 1 Screening Day -28 to-1	Visit 2 Baseline Day 1	Visit 3 Phone Day 15 ±1	Visit 4 In Clinic Day 29 ±2	Visit 5 In Clinic Day 43 ±2	Visit 6 In Clinic Day 85 ±3	Visit 7 In Clinic / End of Acthar Taper Day 113 ±3	Early Termination
Hepatitis Serology ^d	X							
IGRA for TB	X							
Immunological protein assay ^e	X	X				X		X
IXRS contact	X	X		X	X			X
Study Therapy								
Study drug and injection record training		X						
Dispense study drug		X		X	X			
Administer first dose in clinic ^f		X						
Adverse event assessment	X	X	X	X	X	X	X	X
Injection record review				X	X	X	X	X
Concomitant treatment review		X	X	X	X	X	X	X
Start Acthar Taper						X		
End Acthar Taper							X	
Study exit							X	X

AE = adverse events; ET = early termination; HbA1c = glycosylated hemoglobin; IDEEL = Impact of Dry Eye on Everyday Life; IGRA = Interferon gamma release assay; IOP = Intraocular Pressure; ODS = Ocular Discomfort Score; TB = tuberculosis; VAS = Visual Analogue Scale.

^a Height at screening only. Weight at screening, Visits 2, 6, and ET.

^b Blood pressure, respiratory rate, pulse rate and body temperature. For blood pressure, an average of 2 readings after the subject has been seated for \geq 5 minutes at the Screening and Baseline Visits. Single readings after subject has been seated for \geq 5 minutes at all other time points.

^c Refer to Section 9.2.

^d HBsAg, HBcAb, and HCV.

^e Refer to Table 2.

^f The first dose will be administered at the clinic and the subject should be observed for at least 1 hour after dosing.

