2.3. Outcome Measures

The primary outcome measure is the proportion of responders who improved on the IDEEL score. There are no secondary outcome measures.

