4.2. Exclusion Criteria

A subject is ineligible for study participation if the subject meets any of the following criteria at the Screening or Baseline Visit:

1. Subject is from a vulnerable population, as defined by the US CFR Title 45, Part 46, Section 46.111(b) and other local and national regulations, including but not limited to, employees (temporary, part-time, full time, etc.) or a family member of the research staff conducting the study, or of the sponsor, or of the clinical research organization, or of the IRB/IEC;
2. Have any ocular condition that, in the opinion of the investigator, could affect study parameters including, but not limited to, glaucoma, diabetic retinopathy, blepharitis, meibomian gland disease, lid margin inflammation, ocular allergies, follicular conjunctivitis, iritis, uveitis, neuropathic pain and/or active ocular inflammation not related to keratitis;
3. Have a history of laser-assisted in situ keratomileusis (LASIK) or similar type of corneal refractive surgery within 12 months prior to the Baseline visit, and/or any other ocular surgical procedure (eg, cataract surgery, eyelid surgery) within 12 months prior to the Baseline Visit; or any scheduled ocular surgical procedure during the study phase;
4. Have active or any history of ocular herpes; and other ocular infection within 30 days prior to the Baseline visit;
5. Have current punctal plugs (within 30 days prior to Screening visit), punctal occlusion, or history of nasolacrimal duct obstruction;
6. Be unwilling to avoid wearing contact lenses for 7 days prior to the Screening visit and for the duration of the study phase;
7. Have best corrected visual acuity < 0.7 Logarithm of the Minimum Angle of Resolution (logMAR) in each eye at the Screening and Baseline Visits;
8. Use prohibited prescription or over-the-counter (OTC) medications or devices and be unable to discontinue their use for the required period before entry into the study as follows:

- a. Ophthalmic cyclosporine (Restasis®) or ophthalmic lymphocyte function-associated antigen-1 (LFA-1) antagonist (Xiidra®): 12 weeks prior to the Screening visit;
- b. Corticosteroids (topical and systemic), ocular autologous serum, antibiotics (topical and systemic), mast cell stabilizers (topical and systemic), vasoconstrictors (topical and systemic): 30 days prior to the Screening visit;

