- c. Systemic tetracycline compounds (tetracycline, doxycycline or minocycline), unless the dose has been stable for at least 30 days prior to the Screening visit and will remain stable during the study phase, in which case this is permitted;
- d. Any medication (topical and systemic) known to cause ocular drying, such as the use of systemic anticholinergic medications (eg, antihistamines and antidepressants), unless the dose has been stable for at least 30 days prior to the Screening visit and will remain stable during the study phase;
- e. Antihistamines (topical and systemic): 7 days prior to the Screening visit;
- f. Topical or nasal vasoconstrictors within 14 days prior to screening;
- g. Unable to refrain from using artificial tears
- h. Subject has received glucocorticosteroid implants such as Retisert®, Iluvien®, or Yutiq™ within 3 years prior to the Baseline Visit or has had complications related to the device and/or subject has had a glucocorticoid implant removed within 90 days prior to the Baseline Visit or has had complications related to the removal of the device;
 - i. Any FDA-approved medical devices other than punctal plugs (eg Lipiflow® and Truetear®) for dry eye 12 weeks prior to the Screening visit;
- 9. Subject is unwilling to receive, or is intolerant of, SC injections;
- 10. Subject has a history of sensitivity to ACTH preparations or sensitivity to porcine protein products;
- 11. Subject has Type 1 or Type 2 diabetes mellitus or is taking antidiabetic medication (a history of gestational diabetes mellitus is not exclusionary);
- 12. Subject has proliferative or severe nonproliferative diabetic retinopathy, clinically significant macular edema due to diabetic retinopathy, or neovascular/wet age-related macular degeneration;
- 13. Subject has a history of chronic active hepatitis including active or chronic hepatitis B, or acute or chronic hepatitis C;
- 14. Subject has a history of tuberculosis (TB) infection, any signs/symptoms of TB, or any close contact with an individual with an active TB infection;
- 15. Subject has an active corneal infection, any other systemic infection;
- 16. Subject has received a live or attenuated-live vaccine within 30 days prior to screening;
- 17. Subject had ocular trauma, penetrating intraocular surgery, refractive surgery, corneal transplantation, or eyelid surgery within 12 weeks prior to screening;

18. Subject is unwilling to abstain from eyelash growth medications for the duration of the trial;

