5.6.1. Permitted Concomitant Therapies

Permitted concomitant medications include lid hygiene, warm compresses and artificial tears or any medication not mentioned in the exclusion criteria provided the subject has been on a stable dose for at least 4 weeks prior to the Screening Visit. Patients should be instructed not to use ophthalmic preparations 2 hours prior to each study visit.

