8.2. Populations for Analysis

For the purposes of analysis, the following populations are defined

- The Modified Intent-to-Treat (mITT) population will include all subjects who receive at least 1 dose of study drug and who contribute any postbaseline efficacy data to the study.
- The Per-Protocol (PP) population will include a subset of the mITT population with subjects who do not have any major protocol deviations.
- The Safety Population will include all subjects who receive 1 or more doses of study drug.

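### Exclusion 8g on artificial tears gives no period and is not reconciled with section 5.6.1, and if tears are allowed on study nothing limits starting or increasing them between the Day 1 and Day 85 IDEEL

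*Combined protocol and SAP*

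**What the plan says.** Exclusion item 8 in section 4.2 concerns users of listed products who would "be unable to discontinue their use for the required period before entry into the study". Item 8g reads in full "Unable to refrain from using artificial tears". It supplies no period. The neighbouring items do: 8a, 8b, 8e, 8f, 8h and 8i each give a time window. Items 8c and 8d instead set a stability condition; 8c, for example, requires a dose that "will remain stable during the study phase, in which case this is permitted".

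Section 5.6.1 lists the permitted treatments. Besides two non-drug lid measures, it names "artificial tears or any medication not mentioned in the exclusion criteria provided the subject has been on a stable dose for at least 4 weeks", counted back from Screening. It adds: "Patients should be instructed not to use ophthalmic preparations 2 hours prior to each study visit". Section 5.6.2, the list of treatments prohibited from Baseline through Visit 7, does not mention tears.

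Section 5.6 has dose and frequency of concomitant medications recorded from Screening through Visit 7. Table 1 schedules "Concomitant treatment review" at Baseline and every later visit.

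On the outcome, section 2.3 states: "The primary outcome measure is the proportion of responders who improved on the IDEEL score". There are no secondary outcome measures. Section 8.2 defines the Per-Protocol population as "a subset of the mITT population with subjects who do not have any major protocol deviations".

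**The concern.** Two problems follow.

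The first is eligibility. Section 4 allows no waivers, and about six sites must each decide what 8g requires. A site that reads it as abstinence, a site that reads it as a washout and a site that reads it as a pre-visit restriction could admit different subjects.

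The second is the outcome. Artificial tears treat the symptoms that the IDEEL symptom bother module scores. With no control arm, a subject who starts tears or uses more of them after Day 1 and then scores better can be counted as a responder, and nothing in the design offsets that. The protocol writes an on-study stability condition for the drugs in 8c and 8d but writes none for tears.

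**Working it through.** No planned figure is involved, so the check is mainly a comparison of texts, followed by arithmetic for scale.

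**Readings of 8g against 5.6.1**

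| Reading of 8g | Fit with 5.6.1 | Tear use after Day 1 |
|---|---|---|
| Abstinence for the whole study | Contradicts the permission | Held at none |
| Washout before entry | Compatible on study, but the length is not given; a washout starting before Screening would also clash with the 4-week stable-dose proviso, if that proviso covers tears | Not limited |
| Able to abstain for 2 hours before visits | Agrees, and the period is defined | Not limited apart from those 2 hours |

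The third reading fits the item 8 stem imperfectly, because the stem speaks of a period before entry. The missing stability rule exists only under the second and third readings. It should not be added to the contradiction, which belongs to the first.

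**Rules that might limit tear use on study**

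- The stable-dose proviso in 5.6.1 looks back from Screening. The sentence also leaves open whether it attaches to tears or only to other medications.
- The 2-hour rule limits timing, not amount. It applies equally at every visit.
- Section 5.6 and Table 1 record use but do not restrict it.
- The Per-Protocol population removes major deviations. A change in tear use that breaks no stated rule would not ordinarily be one. That is an inference, since the text does not define a major deviation.

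**Exposure interval.** The Table 1 row for IDEEL is blank at Screening and marked at Days 1, 15, 29, 43 and 85 and at Early Termination. That gives one pre-treatment value and four scheduled later ones, over 85 − 1 = 84 days. The protocol does not name Day 85 as the primary timepoint; it is the last scheduled IDEEL.

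**Scale.** The documents give no frequency of tear changes. Assume, for illustration only, that 1 to 3 subjects are reclassified in one direction:

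- n = 30 (planned analysable number, section 8.1): 1/30 = 3.3 points; 3/30 = 10.0 points.
- n = 36 (maximum enrolled): 1/36 = 2.8 points; 3/36 = 8.3 points.

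For comparison, the exact (Clopper-Pearson) 95% interval for an assumed 15/30 is 31.3% to 68.7%. The half-width is (68.7 − 31.3)/2 = 18.7 points, or 0.187 × 30 = 5.6 subjects. For an assumed 9/30 the interval is 14.7% to 49.4%, with a half-width of 17.3 points from unrounded limits, or 5.2 subjects. So between 5 and 6 of 30 subjects would have to move the same way to match sampling error. These are 1/n figures that would hold for any uncontrolled factor. They say nothing about how often tear use changes.

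**The case against.** The strongest reply is that one reading already harmonises the text: a subject may use tears but must be able to abstain for 2 hours before each visit. That is correct. A reader might infer that 8g flatly contradicts 5.6.1, and the documents do not support that as the only meaning. What stands is that 8g does not point to the 2-hour rule, and its stem points elsewhere.

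A reader might also infer that the responder proportion is biased upward. The clearest upward route, tears withheld for Day 1 and then resumed, needs the washout reading. The 2-hour rule cannot produce it. Tear use may also fall: a subject who feels better may use fewer drops, which could lower the measured improvement. The documents therefore support neither a size nor a net direction.

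Three further points have weight. Requiring tear use to stay entirely unchanged would oblige improving subjects to keep using drops, and reduced use may itself reflect benefit, so the rule should allow reductions. Tear use is already recorded, so changes would be visible to an analyst who looked. And this is an exploratory, single-arm Phase 4 study with an empirically chosen sample size and nominal p-values, which limits how much any one conduct rule matters. The separate SAP named in section 8.3 is not in the text available and may contain an analysis rule. Eligibility and conduct rules, however, belong in the protocol.

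**Conclusion.** The point holds as a minor one, worth considering. Item 8g lacks a period and is not reconciled with 5.6.1, so sites could apply it differently. If tears are allowed on study, starting or increasing them between Day 1 and Day 85 is unrestricted, and any resulting improvement can count toward the only outcome measure. This rests on two assumptions: that 8g is not meant as abstinence throughout the study, and that more tear use can improve an IDEEL score. The net effect cannot be sized or signed from the documents.

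A reader might go further and conclude that a tear rule would let response be credited to the drug. It would not. The study would remain uncontrolled and open-label, and the rule would remove one avoidable source of change.

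**What to change.** Replace 8g and the tear wording in 5.6.1 with a single rule:

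- Artificial tears are allowed if product and frequency were stable over the 4 or more weeks preceding Screening.
- Subjects should not start, switch or increase tears through Visit 6. Reductions are allowed and recorded.
- Subjects must be able to go without tears for 2 hours ahead of each visit.

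Using the concomitant treatment data already collected, report a sensitivity analysis of the responder proportion that counts subjects who start or increase tears after Day 1 as non-responders. Report alongside it how many subjects reduced or stopped tears.

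The cost is two wording edits, a minor restriction on subjects and one extra table. No new data collection is needed, because section 5.6 and Table 1 already provide for it.

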4.3. Screen Failures

Screen failures are defined as subjects who consent to participate in the clinical study but are not subsequently treated.

Subjects will be allowed to repeat any single screening assessment/procedure once, if necessary, if it is within the screening window. However, laboratory results indicating a positive or indeterminant TB test, positive hepatitis B surface antigen, hepatitis B core antibody and positive or indeterminant hepatitis C antibody cannot be rescreened. The subject will not be considered a screen failure unless the repeat assessment/procedure result does not meet eligibility criteria. The period from the start of screening related procedures at the Screening Visit to the Baseline Visit must not exceed 28 days, inclusive of any repeat screening procedures.

Subjects who do not meet all of the eligibility criteria at the Screening or Baseline Visits will be deemed a screen failure and the reason for screen failure will be documented.

Rescreening

A subject who is a screen failure at the Screening or Baseline Visit may be rescreened. The subject must repeat all screening procedures. The period from the start of rescreening related

procedures to the first dose of study drug must not exceed 28 days. Subjects may be rescreened only once.

5. STUDY TREATMENT

Acthar is a naturally sourced complex mixture of adrenocorticotrophic hormone (ACTH) analogues and other pituitary peptides used to provide a prolonged release after intramuscular or subcutaneous (SC) injection. Acthar contains 0.5% phenol, not more than 0.1% cysteine (added), sodium hydroxide and/or acetic acid to adjust pH, and water for injection.. Acthar is currently labeled for use in keratitis ([Acthar® Gel Package Insert, 2019](#)). Acthar is supplied as 5 mL multidose vials containing 80 U of ACTH per mL.

5.1. Treatment Administration

Following a screening period of up to 28 days, subjects who meet entry criteria will be treated with Acthar 1 mL (80 units [U]) subcutaneously (SC) 2x (twice) per week for 12 weeks. After this 12 week period of treatment with 80 U, Acthar will be tapered over a 4 week period. The 80 U dose will be reduced to 40 U 2x/week for 2 weeks, followed by 40 U 1x/week for 2 additional weeks. An in-clinic safety visit will also take place 4 weeks after the last treatment dose. The subject or subject's caregiver will receive training/instructions and will administer the first dose of study drug in the clinic under the supervision of study staff. The subject will remain in the clinic for at least 1 hour postdose to monitor for allergic, including anaphylactic, reactions. Thereafter, all doses will be administered by the subject or the subject's caregiver at home. If a subject misses a dose, that dose will be skipped and the reason for the missed dose will be recorded.

5.2. Study Treatment Preparation/Handling/Accountability

Study treatment will be provided by the sponsor or sponsor's representative and will be labeled as required by local and national regulations.

Acthar is supplied as 5 mL multidose vials. Acthar vials contain 80 U of ACTH per mL. The vials should not be over pressurized prior to withdrawing the product. The vials should be warmed to room temperature before using.

The investigator or designee will confirm that appropriate temperature control conditions have been maintained during transit for all study treatments received and any discrepancies are reported and resolved prior to study treatment administration.

The study treatment will be maintained in a monitored, environmentally controlled (in accordance with treatment labeling), secure, locked area with restricted access at the study site.

Only subjects enrolled in the study will receive study treatment and only authorized study staff will dispense study treatment.

In accordance with the International Council for Harmonisation (ICH) requirements, at all times the investigator will be able to account for all study treatment furnished to the study site. An accountability record will be maintained for this purpose. The investigator must maintain accurate records indicating dates and quantity of study treatment received, to whom it was administered (subject-by-subject accounting) and accounts of any study treatment accidentally or deliberately destroyed. All unused study treatment not involved in immediate subject treatment will be maintained under locked, temperature-controlled storage at the study site.

5.3. Storage of Clinical Supplies

Study drug will be supplied in kits containing the appropriate amount of vials. Study drug will be stored under refrigeration between 2° to 8°C (36° to 46°F). Please refer to the Pharmacy Manual for complete information regarding handling, storage, preparation, and accountability of study treatment.

5.4. Measures to Minimize Bias

This is an open label study, no randomization or stratification will be employed in treatment assignment.

5.4.1. Interactive Phone/Web Response System

The investigator or designee will contact interactive phone/web response system (IXRS) to register subjects at screening. The subject's identification (ID) number will be determined by the IXRS and will be used to identify the subjects for the duration of the study within all systems and documentation.

Each subject will be assigned a unique ID number. If the subject is not eligible to receive study treatment, or should discontinue from the study, the subject ID number will not be reassigned to another subject.

In the event that a subject repeats any evaluation during the screening window, they will not receive a new ID number. In addition, subjects who fail screening and are rescreened will not receive a new subject ID number. At the Baseline Visit, qualified subjects who meet all of the eligibility criteria will be enrolled into the study.

The investigator or designee must contact the IXRS to report a subject as a screen failure if the subject does not meet eligibility criteria prior to enrollment.

The investigator must maintain a subject master log linking the subject ID to the subject's name. The investigator must follow all applicable privacy laws in order to protect a subject's privacy and confidentiality. Information that could identify a subject will be masked on material received by the sponsor.

5.4.2. Emergency Identification of Study Treatment

Not applicable.

5.5. Study Treatment Compliance

Prior to beginning the administration of study treatment, subjects and/or their caregiver will be trained on dosing and mode of administration and must exhibit proper technique. Subjects and/or their caregiver will be trained on the completion of the injection record, will complete study record entries to record all study drug administration and will bring it, along with all study drug kits including used vials, to each visit. Each time study treatment is dispensed compliance will be emphasized. Injection record training is an ongoing process, as the record will be reviewed with the subject at each visit to monitor compliance with study drug administration.

5.6. Prior and Concomitant Therapy

The start and stop date, dose, unit, frequency, route of administration, and indication for all prior (taken within the 30 days prior to the Screening Visit) and concomitant (taken from the Screening Visit through Visit 7) medications and nondrug therapies (eg, blood transfusions, oxygen supplementation, physical therapy, etc) received will be recorded.

In addition, all prior treatments for severe keratitis administered be recorded with start and stop date, dose, unit, frequency and route of administration.

